Address	

3. Delegation of Clinical Trial Duties

Responsibilities for the conduct and oversight for the trial are delegated to you as the Coordinating Principal Investigator. You may delegate trial related responsibilities to the listed

Principal Investigator(s) and any trial-related personnel. All trial-related duties delegated by the Coordinating Principal Investigator or Principal Investigator(s) and trial-related personnel must only be delegated to those that are qualified by experience and training. Delegated responsibilities must be retained in the [UNSW Clinical Trial Delegation Log](#). The UNSW Sponsor's Delegate is to be notified of the following:

- Protocol deviation reports outlined in the UNSW Research Misconduct Procedure.
- Any serious breach of Good Clinical Practice, the clinical trial protocol, the clinical trial standard operating procedures, or the human ethics approval that is likely to affect to a significant degree the safety or rights of participants or the reliability and robustness of the data generated in the clinical trial.
- Significant safety issues that are likely to (or have the potential to) affect to a significant degree the safety or rights of participants or the reliability and robustness of the data generated in the clinical trial.
- Urgent safety measures implemented to remove or prevent a significant safety issue.
- Safety reports relating to the continuation, suspension, or discontinuation of the clinical trial for safety reasons.
- Non-compliance with the protocol, SOPs, GCP, and applicable regulatory requirement(s) significantly affects or can potentially affect human subject protection or reliability of trial results significantly.
- Participant complaints or concerns received concerning the conduct of the research.
- Significant modifications to the clinical trial are likely to affect a significant degree the safety or rights of participants or the reliability and robustness of the data generated in the clinical trial.
- Addition of participating trial sites, contractual arrangements at participating sites or modifications to legal agreements.
- The intention to conduct the trial in other countries.

4. Trial Objectives and Purpose

This clinical trial aims to investigate the effectiveness of a Cognitive Behavioural Therapy (CBT) program delivered via a smartphone application (called *ClearlyMe*) for improving mental health outcomes in Australian adolescents (aged 12 to 17 years) with mild to moderate depressive symptoms.

This trial will examine the effectiveness of a new CBT smartphone application (*ClearlyMe*) for reducing depressive symptoms in adolescents when compared to guided use and an active-attention matched control condition.

The primary outcome is depressive symptoms, measured by a change in self-report symptoms between baseline and 6-weeks post-baseline (primary endpoint). Secondary mental health outcomes include improvements in anxiety symptoms, psychological distress and emotional wellbeing between baseline and 6-weeks post-baseline as measured by validated self-report scales. Follow-up outcomes will be evaluated at 4-months post-baseline (secondary endpoint) using the same self-report scales to determine whether effects are sustained in the mid-term and whether the interventions are associated with any delayed benefits or harms.

The primary research questions that this trial seeks to address are:

1. What is the effectiveness of *ClearlyMe* (both self-directed and guided use) for reducing depressive symptoms?

Secondary research questions include:

2. What is the effectiveness of *ClearlyMe* for reducing anxiety symptoms, psychological distress, rumination, and improving emotional wellbeing, quality of life, emotion regulation, and CBT skill acquisition?
3. Does guided support lead to greater engagement with and completion of the *ClearlyMe* app when compared to self-directed use?
4. Do factors such as gender, age, baseline mental health history or symptom severity, perceived need for care or openness to digital mental health, moderate the improvements in depressive symptoms found among users of *ClearlyMe*?
5. Do factors such as rumination, emotion regulation, CBT skill acquisition, digital therapeutic alliance and program engagement/completion mediate the improvements in depressive symptoms found among users of *ClearlyMe*?

Primary and Secondary Hypotheses:

This trial will determine whether the *ClearlyMe* smartphone application is effective for lowering depressive symptoms when compared to guided use and an active attention-matched control in symptomatic adolescents. It is hypothesised that:

H1= Participants who receive *ClearlyMe* (both self-directed and guided use) will report greater reductions in depressive symptoms between baseline and primary endpoint as well as baseline and secondary endpoint when compared to participants in the control condition;

H2= Participants who receive *ClearlyMe* (both self-directed and guided use) will report greater improvements in secondary outcomes (anxiety, psychological distress, emotional wellbeing,

quality of life, rumination, emotion regulation and CBT skill acquisition) between baseline and primary endpoint as well as baseline and secondary endpoint when compared to participants in the control condition;

H3= Participants' engagement with and completion of *ClearlyMe* will be significantly higher among participants who receive guided support when compared to participants who receive self-directed use.

Other exploratory hypotheses:

H4= Improvements in depressive symptoms among users of *ClearlyMe* will be moderated by gender, age, history of mental health, symptom severity at baseline, greater perceived need for care and higher levels of openness to digital mental health.

H5= Improvements in depressive symptoms among users of *ClearlyMe* will be mediated by rumination, emotion regulation, CBT skill acquisition, digital therapeutic alliance, and rates of engagement/completion.

5. Background Information

Adolescence is a significant and sensitive stage of life, whereby individuals evolve physically, socially, and psychologically as they transition to adulthood (Dahl et al., 2018). Given the rapid changes in a young person's development, this period also presents important risks and opportunities for young people's mental well-being. For example, a young person's access to a supportive environment, ability to maintain healthy sleeping and exercise behaviours, learn and develop coping, problem solving, emotional and interpersonal skills can influence their mental health (WHO., 2020). Poor mental health can have detrimental consequences to a young person's quality of life and their ability to function socially and academically (McGorry et al., 2011; Patel et al., 2007). Recent research suggests the global prevalence of depressive and anxiety symptoms in children and adolescents during the COVID-19 pandemic has increased, with 1 in 4 experiencing elevated depressive symptoms and 1 in 5 experiencing elevated anxiety symptoms, highlighting the need for mental health care (Racine et al., 2021).

In a recent national survey, Australian young people reported mental health as being the most important issue and within their top three concerns (Carlisle et al., 2019). However, despite mental health being at the forefront of young people's minds, many continue to experience help-seeking barriers including stigma, negative beliefs about mental health services, preference for autonomy and accessibility factors (cost, transport, waiting times) (Aguirre Velasco et al., 2020). Interventions delivered via digital platforms have the potential to overcome many of these barriers. The COVID-19 pandemic has highlighted the demand for mental health digital interventions when accessibility factors are disrupted. Recent data showed that registration to an Australian digital CBT-based mental health program (This Way Up) during the COVID-19 period increased 500% compared to the previous year (Mahoney et al., 2021). Similarly, the use of mental health apps rose by over 200% during lockdown (ORCHA Health, 2021). However, not all digital mental health products are created equal. With approximately 20,000 mental health apps on the market, many do not incorporate evidence-based therapeutic techniques and lack

sufficient evidence to be endorsed as treatment for adolescents (Wasil et al., 2019). This is problematic as programs that are not evaluated may cause unintended adverse effects including misinformation, privacy breaches, inadequate support or worsening symptoms. Therefore, it is important that young people have direct access to evidence-based, safe, effective treatments.

Digital interventions based on Cognitive Behavioural Therapy (CBT) have been shown to be effective for children and adolescents with anxiety (Hedge's $g = 0.51$) and depression symptoms (Hedge's $g = 0.44$) when compared to passive controls (Christ et al., 2020). However, many of the credible digital interventions publicly available have been designed for adults, which means they might not be engaging or include appropriate, or relevant examples for young users. Given low adherence and engagement to digital interventions is common, it is important that products are well-matched to the needs of the individual using them to ensure they are appealing to use. Human support, guidance, or encouragement has been associated with increased adherence to digital interventions (Beatty & Binnion, 2016). However, in studies of computerised CBT with young people, the impact of support on depression and anxiety outcomes is mixed in terms of the optimal amount, or type of support provided (Ebert et al., 2015; Pennant et al., 2015; Podina et al., 2016).

The *ClearlyMe* smartphone application was developed to address the need for an adolescent-focused, evidence-based and evaluated mobile mental health intervention. *ClearlyMe* was created through an extensive, iterative co-design process with a multidisciplinary team at the Black Dog Institute in collaboration with young people, mental health professionals, and parents. The smartphone app is based on CBT and is delivered through a vibrant, youth-friendly visual identity. Therefore, this study aims to determine whether the *ClearlyMe* app reduces the severity of depressive symptoms in young people.

6. Statement of Compliance

The clinical trial will be conducted in compliance with the following guidelines and documentation:

- [ICH Guidelines for Good Clinical Practice \(GCP\)](#)
- [National Statement on Ethical Conduct in Human Research](#) (National Statement)
- As approved by the Human Research Ethics Committee (HREC), the clinical trial protocol is responsible for monitoring the trial's conduct.
- The responsibilities set out by the UNSW Sponsors Delegate.
The onsite or remote monitoring standard operating procedures as put in place by the clinical trial sponsor.

7. Trial Design

This study will utilise a three-arm randomised controlled trial, conducted entirely online via the Black Dog Institute Research Engine. Data will be assessed at baseline, primary endpoint (6-weeks post-baseline) and secondary endpoint (4-months post-baseline). This methodology is appropriate to meet the research aims because RCTs are considered to provide the most reliable evidence on the effectiveness of interventions because the processes used during the conduct of this type of trial minimise the risk of confounding factors influencing the results. Because of this, the findings generated by RCTs are likely to be closer to the true effect than the findings generated by other research methods (Akobeng, 2005).

Randomisation will be carried out according to the International Council for Harmonisation (ICH) guidelines. Randomisation to one of the three trial arms will be conducted immediately after completion of the baseline assessment using a computerised randomisation procedure within the Black Dog Institute Research Engine. Stratified randomisation approach with a block size of 6 (1:1 ratio) will be used to ensure balance across the conditions in terms of age (12 to 14 years vs. 15 to 17 years), ~~gender (male vs. female)~~, and symptom severity (mild [as determined by a total score of 9 or less on the PHQ-A] vs moderate to moderately-severe [as determined by a total score of 10 or more on the PHQ-A]). Allocation will be fully automatic, with no interference from the research team.

Blinding – Participants: All study materials will refer to the interventions being examined as “smartphone activities and information for your mental health”. While participants will be aware of which smartphone activity they will be required to use (due to the PICF and instructions for use provided), they will not be directly informed of their condition allocation (i.e., intervention 1 vs. intervention 2 vs. control).

Blinding – Statistician: The statistician involved in examining the effects of the conditions of primary and secondary outcomes will not be informed of participants’ specific intervention allocation. Condition allocated will be marked as “Condition A, Condition B, Condition C” to ensure the statistician remains blinded to participants’ intervention upon primary and secondary analysis of the results. All other potential markers of allocation will be removed from the data analysis file. Upon completion of these analyses, the statistician will be become unblinded when examining mediators and moderators as well as intervention completion rates, due to differences in the total number of modules/lessons across each condition. This data will only be reviewed by the trial statistician upon completion of the primary and secondary outcomes.

Blinding – Chief Investigators, Trial Manager and Research Officers/Assistants: The chief investigators, trial manager and research assistants will be unblinded to participants’ allocation as they will have access to the Black Dog Institute Research Engine to contact participants if they experience adverse events, and to provide support to participants allocated to the “guided use” condition. They will also be responsible for downloading and cleaning the data extract. The Chief Investigators, Trial Manager, and Research Officers/Assistants will not be involved in data analysis of the primary and secondary outcomes.

For the study outputs, a CONSORT flow diagram will be provided outlining study recruitment, including n for each stage.

8. Sample Size

The total baseline sample size required for detecting change in the primary outcome is 489. This is based on calculations using $\alpha=0.05$, power=0.8, small to medium effect sizes for psychoeducation ($d=0.10$), self-directed CBT ($d=0.35$), and guided CBT ($d=0.65$) on depressive outcomes at primary endpoint and a 20% attrition rate between baseline and primary endpoint.

Specifically, this sample size is comprised of the following sample sizes for each of the participant groups:

1. Trial Arm 1=163 participants
2. Trial Arm 2=163 participants
3. Trial Arm 3=163 participants.

This sample size is sufficient to meet the research aims and answer the research questions because the power calculation reveals that this sample size will allow for statistically significant results. As this trial will be conducted entirely online via the Black Dog Institute Research Engine, no specific trial sites will be established.

9. Selection and Withdrawal of Subjects

All inclusion and exclusion criteria will be assessed through a self-report screening assessment hosted on the study website. Excluded participants will be provided with a generic message and details on youth mental health services and other trusted mental health organisations. Participants will be provided with information on where to seek help and self-care activities. More information on the screening protocol is outlined in Section 9.4 and Appendix A.

To mitigate the potential of participants “gaming” the inclusion criteria (i.e., making multiple attempts to enter the study by various combinations of the inclusion/exclusion criteria), the Participant Information Statement and Consent Form (PISCF) will not stipulate the exact details of the inclusion and exclusion criteria for depressive scores, and will instead give generalised indications.

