10.1 Trial Interventions

Trial Arm 1. Intervention 1 – Self-directed CBT smartphone application *ClearlyMe*: Participants allocated to this condition will receive *ClearlyMe*. *ClearlyMe* is a free, self-directed CBT-based smartphone application that provides therapeutic content and symptom management strategies to adolescents experiencing mild to moderate depressive and anxiety symptoms. The application was specifically designed for adolescents by a multidisciplinary team of psychologists, researchers, user experience designers and software developers at the Black Dog Institute. *ClearlyMe* is delivered as an autonomous, non-sequential CBT program consisting of 37 brief lessons (i.e., therapeutic content alongside activities). Lessons include the following evidence-based treatment components: psychoeducation, cognitive restructuring, emotion awareness and acceptance, goal setting, problem solving, activity scheduling, behavioural activation, exposure, relaxation, mindfulness, and values labelling. The lessons also encourage participants to practise the psychological skills in-between lessons and return to the app to reflect or access further content as needed. The lessons vary in length, taking between 5 to 10 minutes each to complete. To help navigate the program content, users are encouraged to complete the lessons via nine curated ‘collections’. A collection is defined as a structured selection of related lessons grouped together with a brief title and introduction. Each collection varies in length, taking approximately 20 minutes to complete. Users can also complete the individual lessons from a ‘show all’ list whereby they self-select lessons considered to be relevant to their individual needs. In this list, lessons are categorised into three groups depending on their target: ‘emotions’, ‘thoughts’, ‘behaviours’. The app also includes a Moodcheck (i.e., brief mood monitoring), Mind Hacks (i.e., quick strategies that help in the moment), and Stories (i.e., short videos of young peoples’ experience managing mental health symptoms and positive help-seeking experience) to provide users with additional pathways to accessing therapeutic content. For these features, specific lessons are recommended after the feature is accessed. *ClearlyMe* also includes in-app reminders, ‘saving’ and ‘favourite’ functions to support users to return to the app to reengage in content. In-app reminders include a ‘revisit the app’ reminder, which notifies all participants to use the app if they haven’t done so in the past 7 days. This reminder is locked and cannot be turned off in the app. Users can also set an additional reminder to use the Moodcheck feature once a day for as many days as they wish. Due to the developer requirements of iOS app store and Google Play, app notifications must be able to be disabled in a user’s phone settings. The app also includes a ‘Get Help’ section that contains information of when and where to access additional mental health support services (e.g., Kid’s Helpline). Appendix E includes the full product information. To ensure compliance, participants who fail to download the *ClearlyMe* app within 7 days of randomisation will be sent an email and SMS reminder to download the app.

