
Participant instructions for use: In this trial, participants are provided with access to *ClearlyMe* for 6-weeks. Participants are instructed to complete the app content by undertaking at least one collection per week (approximately 20 minutes) for the intervention period; however, participants can complete the app content in any order and according to their preferences. Participants are also instructed to use the ‘Get Help’ section of the app if they feel they require extra mental health support during the intervention period, although this section of the app is not monitored in real-time by the research team. To further ensure compliance, all participants in this intervention arm will be sent one SMS per week from the Black Dog Institute Research Engine reminding them to use the *ClearlyMe* app. Participants allocated to this intervention arm will not receive any additional human

contact from the research team, unless technical support for the smartphone application (via email) is required.

Trial Arm 2. Intervention 2 – Guided use of CBT smartphone application *ClearlyMe*: Participants allocated to this condition will receive the same intervention provided in Trial Arm 1, with the addition of a weekly guided support session. This will take place in the form of a SMS chat provided by the research team for the duration of the intervention period. Participants will be contacted via SMS on their mobile phone number at the times provided to participants after randomisation (4pm to 7pm Monday to Friday). Contact will be made weekly, with one additional attempt made for non-response (two days apart, total of 2 contact attempts in 7 day period). In total, participants in this condition will receive 6 weekly support sessions in the intervention period. Personnel conducting the guided sessions will be research employees of the Black Dog Institute and will use a standard script, with a decision flow chart to direct the chat (see Appendix F). The SMS chat will consist primarily of technical support with some low intensity motivational coaching. Research Assistants (RAs) not clinicians, will be trained to conduct these sessions and will be supervised by a clinician. The clinician will be available during these sessions to support the RA if needed. The guided support sessions will be designed to be conducted in one sitting (i.e., within 20 minutes) but duration and script compliance will be recorded by the research assistants.

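### The statistician is unblinded more widely than the stated reason supports: lesson totals reveal the control but not which app arm is guided, and they play no part in the moderator tests

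*Protocol*

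**What the plan says.** The protocol's Section 7 (Blinding – Statistician) codes the arms as Conditions A, B and C "to ensure the statistician remains blinded to participants’ intervention upon primary and secondary analysis of the results". Once those analyses are done, "the statistician will be become unblinded when examining mediators and moderators as well as intervention completion rates", and the reason given is "due to differences in the total number of modules/lessons across each condition". The same paragraph adds that the statistician sees these data only after the primary and secondary outcomes are finished.

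Section 4 groups H1 to H3 under the primary and secondary hypotheses. H3 is directional: engagement and completion "will be significantly higher among participants who receive guided support when compared to participants who receive self-directed use". The label "Other exploratory hypotheses" comes after H3 and covers H4 (moderation) and H5 (mediation).

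Section 10.1 describes the app as an "autonomous, non-sequential CBT program consisting of 37 brief lessons". Of Arm 2 it says: "Participants allocated to this condition will receive the same intervention provided in Trial Arm 1", with a weekly SMS chat added. Arm 3 receives six weekly psychoeducation modules.

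**The concern.** One reason is given for unblinding several different analyses. It fits a comparison of completion across all three arms, because the totals give the control away. It does not obviously fit H3, which compares two arms with identical app content, or H4, whose moderators have nothing to do with how many lessons an arm contains.

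What is at stake is analyst discretion. Under Section 7 the chief investigators, trial manager and research staff all know the allocation, and they also download and clean the data. The statistician is the one masked analysis role. Section 10 lists seven kinds of app usage data from which engagement and completion could be built, and H3 predicts which arm will do better. An analyst who knows which arm is guided could, without intending to, lean towards the definition that favours it.

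**Working it through.** The plan states no figure to reproduce. The check is which arms the lesson totals can tell apart, and which analyses depend on those totals.

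**Inputs**

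| Arm | Content | Total | Source |
|---|---|---|---|
| 1, self-directed | app | 37 lessons | Section 10.1 |
| 2, guided | same app plus weekly SMS chat | 37 lessons | Section 10.1 |
| 3, control | psychoeducation by SMS | 6 modules | Section 10.1 |

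**Step 1: what the totals reveal.** Three masked labels can be assigned to three arms in 3! = 3 × 2 × 1 = 6 ways. Suppose the statistician sees totals of 37, 37 and 6. The label with 6 must be the control (1 way). The other two labels can be guided and self-directed in either order (2! = 2 ways). So 1 × 2 = 2 assignments remain. The control is known and the two app arms are still interchangeable. The statement that totals differ across each condition is therefore not true of Arm 1 against Arm 2.

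**Step 2: what the usage fields reveal.** Section 10 lists the same app usage fields for Arms 1 and 2 together, and none of them records the SMS chat. Section 10.1 says that chat duration and script compliance are also recorded. Those records exist only for Arm 2, but they are not among the listed usage fields and can be left out of an H3 extract.

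**Step 3: each analysis against the reason.**

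- *H3.* It needs the control set aside, so revealing the control is justified. It does not need to be known which app arm is guided until the result is read.
- *H4.* The six moderators in Section 4 are gender, age, mental health history, baseline severity, perceived need for care and openness to digital mental health. None carries a lesson count, and a condition-by-time-by-moderator model can be fitted on A, B and C. Appendix I also lists digital therapeutic alliance as a moderator. It is measured at the primary endpoint, so not every listed moderator is a baseline variable, but it carries no lesson count either.
- *H5.* Engagement and completion are among the mediators, and there the reason is valid.
- *Adherence analysis (Section 10).* It compares adherers, non-adherers and control. It needs the control identified but does not separate guided from self-directed use.

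The reason thus supports revealing the control for H3, the adherence analysis and the engagement mediator. It does not support decoding guided against self-directed for H3, or any decoding for H4 when all three labels are in the model.

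**The case against.** A reader might infer that the protocol breaks its own blinding rule, since H3 is a secondary hypothesis and secondary analyses are promised masked. The text does not support that. The Section 7 paragraph opens by limiting the blind to effects on primary and secondary outcomes, and completion is not among the outcomes that Section 4 or H2 names. Completion rates are then listed openly as an exception that comes afterwards. The phrase about primary and secondary analysis is looser, but read as a whole the paragraph describes a disclosed, ordered exception.

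A reader might also infer that none of these analyses needs any unblinding. That is too strong. The control must be identified for H3, and also for H4 if it is confined to users of the app, as its wording allows.

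Nor can it be said that completion and adherence cut-offs are left open. Section 10 refers to Appendix D for intervention use, and neither that appendix nor a statistical analysis plan is shown. If the definitions are fixed there, less discretion remains.

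The practical consequence is small. H1 and H2 are finished before the blind is lifted, app usage is extracted automatically so the analyst cannot affect its measurement, and H4 is exploratory. Masking is also imperfect: with the control known, the outcome results by label may let the statistician guess the guided arm, since Section 8 assumes d = 0.65 for guided and 0.35 for self-directed use.

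All of this stands, and it limits the point. It does not supply a reason for decoding the two app arms before H3 is run.

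**Conclusion.** The unblinding in Section 7 is wider than its stated reason supports. Totals of 37, 37 and 6 identify one arm of three. They leave the contrast in H3 masked and have no bearing on the H4 moderators. One of the three non-exploratory hypotheses is affected, together with the exploratory moderation tests. No bias can be quantified from the protocol, and H1 and H2 are unaffected.

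The conclusion rests on two assumptions: that Arm 2's app content is identical to Arm 1's, as Section 10.1 states, and that the H3 extract holds only the usage fields listed in Section 10. It does not depend on whether cut-offs are fixed elsewhere. The change is worth making because it costs little and gives some protection to a directional hypothesis.

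**What to change.** Amend the statistician paragraph in Section 7 to set this order:

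1. After the primary and secondary outcomes, run H4 moderation under A, B and C before any usage data are opened. If H4 is meant to cover app users only, run it after step 2 instead.
2. Reveal only which label is the control.
3. Run H3, and the adherence analysis, with the two app arms still under masked labels. Leave the SMS chat records out of that extract.
4. Unblind fully only for analyses that need arm identity, and name them.

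Keeping the A/B/C labels throughout is the simplest route. If new labels not linked to A/B/C are preferred, participant IDs in that extract must be re-keyed. Section 10 ties usage data to the assessments by the same ID, so the new labels could otherwise be matched back. The moderator lists in Section 4 and Appendix I should be reconciled in the same edit.

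The cost is a few sentences and one extra analysis step or masked extract. No new data are needed. If the team prefers to keep full unblinding for H3, Section 7 should say so and give a reason that applies to the two app arms.
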